7.1.5.2. Incomplete Dates

All AEs with partial onset or stop dates will be identified and the partial dates will be imputed as follows:

- For AE onset date: If day and month are missing but year is available, then the imputed day and month will be 01Jan or the first dosing date of IDELA if they have the same year, whichever is later. If day is missing but the month and year are available, then the imputed day will be the first day of the month or the first dosing date of IDELA if they have the same month and year, whichever is later.
- For AE stop date: If day and month are missing but year is available, then the imputed day and month will be 31Dec or 30 days after the last dose of study treatment if they have the same year, whichever is earlier. If day is missing but the month and year are available, then the imputed day will be the last day of the month or 30 days after the last dose of study treatment if they have the same month and year, whichever is earlier.

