7.1.5. Treatment-Emergent Adverse Events

7.1.5.1. Definition of Treatment-Emergent

TEAEs are events in a given study period that meet one of the following criteria:

- Events with onset dates on or after the start of IDELA and up to 30 days after the permanent discontinuation of IDELA.
- AEs resulting in IDELA discontinuation after the start of treatment.

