Time to onset of AEIs (in weeks) is defined as time from the baseline reference date for safety endpoints to the date of first incident of AEI. In the absence of an event, the onset date will be censored at the earliest from the following dates: last IDELA dosing date (ie, captured on study drug completion CRF page) + 30 days, analysis data cut-off date and death date. Time to resolution of AEIs is calculated as (AEI stop date – start date of first occurrence of AEI + 1) / 7.

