7.4. Concomitant Medications

Concomitant medications will be coded by means of the World Health Organization Drug Dictionary (WHODRUG) dictionary, Q2 2014 into Anatomical-Therapeutic-Chemical classification (ATC) codes.

Concomitant medications are defined as any medications meeting the following criteria

- Starting on or after the baseline reference date for safety endpoints, up to 30 days post the last dose
- Starting before and continuing after the baseline reference date for safety endpoints, up to 30 days post the last dose

The incomplete dates handling method for AE will be used for concomitant medication summaries (Section 7.1.5.2).

Summaries of the number and percentage of subjects who use concomitant medications will be presented in tabular form by preferred drug name based on the FAS. The summary tables will be sorted by descending frequency based on IDELA + R/IDELA treatment group. Subjects will only be counted once for multiple drug use (by preferred drug name).

The summaries and listings of concomitant medications will be based on the FAS.

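### Partial onset dates are moved to the first idelalisib dose without checking whether the event or drug had already stopped

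*SAP*

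**What the plan says.** For an adverse event onset with day and month missing, SAP 7.1.5.2 states that "the imputed day and month will be 01Jan or the first dosing date of IDELA if they have the same year, whichever is later". With only the day missing, the imputed day is "the first day of the month or the first dosing date of IDELA if they have the same month and year, whichever is later". Partial stop dates have their own rule in the same section, but the onset rule never refers to the stop date.

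The first criterion for treatment-emergent status in SAP 7.1.5.1 is "Events with onset dates on or after the start of IDELA and up to 30 days after the permanent discontinuation of IDELA". It uses the onset date alone. The other criterion covers events that lead to idelalisib discontinuation.

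SAP 7.4 then says: "The incomplete dates handling method for AE will be used for concomitant medication summaries". Its first criterion for a concomitant drug is "Starting on or after the baseline reference date for safety endpoints, up to 30 days post the last dose", which uses the start date alone. Its second, "Starting before and continuing after the baseline reference date for safety endpoints, up to 30 days post the last dose", does consider whether the drug continued, but only for drugs whose start precedes the reference date.

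For adverse events of interest, SAP 7.1.7 states: "Time to resolution of AEIs is calculated as (AEI stop date – start date of first occurrence of AEI + 1) / 7".

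Under SAP 3.5.1 and Table 3-1, the safety reference date for both former-placebo groups is the first idelalisib dose, which follows a period on placebo plus rituximab. The protocol's sections on medications and adverse events (9.4.3.3 and 9.4.3.4) contain no date-imputation rule that would modify any of this.

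**The concern.** Moving an uncertain onset to first dose is a sensible cautious choice when the event could have begun on treatment. When the stop date is known to precede first dose, that possibility is gone. The rule then creates an onset later than the end of the event, and the classification steps that follow do not detect it.

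What an affected record does depends on its type:

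- **Any adverse event:** it is counted as treatment-emergent, with relative day 1 in the listings.
- **An adverse event of interest:** it also enters the 0 to <12 week incidence, displaces any genuine later event as the first onset, yields a negative time to resolution, and cuts the subject's person-time in the exposure-adjusted rate (SAP 7.1.8) to almost nothing.
- **A medication:** it is tabulated as concomitant although it stopped before idelalisib. The second criterion in SAP 7.4 would have excluded it, but the imputed start date means the first criterion is met instead.

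The SAP makes this kind of cross-check elsewhere. In 7.3, a partial completion date for the last prior regimen may not fall before that regimen's own start date.

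**Working it through.** The plan gives no figure to reproduce. The check applies the written rules to hypothetical records. All dates below are assumptions for illustration.

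**Rules applied**

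- Imputed onset = later of (1 January or first of the month) and first idelalisib dose, if they share the year (day and month missing) or the month and year (day missing); otherwise 1 January or first of the month.
- Treatment-emergent (onset criterion) = first dose ≤ onset ≤ last dose + 30 days.
- Concomitant = start in that same window, or start before and continuing after first dose.
- Time to resolution in weeks = (stop − onset + 1) / 7. The SAP applies this only to adverse events of interest.

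**Single example.** Onset 2013, stop 10 March 2013, first dose 1 October 2013.

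- Imputed onset: 1 October 2013, relative day 1.
- Days from stop to imputed onset: 21 + 30 + 31 + 30 + 31 + 31 + 30 + 1 = 205.
- Stop − onset + 1 = −205 + 1 = −204 days; −204 / 7 = −29.1 weeks.

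**Five records**, first dose 15 October 2013, last dose 30 June 2015:

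| Recorded onset | Stop | Imputed onset | Treatment-emergent / concomitant | (stop − onset + 1)/7 | With a stop-date check |
|---|---|---|---|---|---|
| 2013 | 20 Mar 2013 | 15 Oct 2013 | yes / yes | −208/7 = −29.7 | 1 Jan 2013; no / no |
| Oct 2013 | 5 Oct 2013 | 15 Oct 2013 | yes / yes | −9/7 = −1.3 | 1 Oct 2013; no / no |
| Sep 2013 | 20 Sep 2013 | 1 Sep 2013 | no / no | 2.9 | unchanged |
| 2012 | 20 Mar 2013 | 1 Jan 2012 | no / no | 63.6 | unchanged |
| 2013 | 20 Dec 2013 | 15 Oct 2013 | yes / yes | 9.6 | unchanged |

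The first two rows are wrong as the rule stands. Rows three and four show that partial dates in an earlier month or year are classified correctly. Row five is the case the rule is meant for, and the check leaves it alone.

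**Size of the shift.** For a year-only onset, the part of the year before first dose from which a record can be moved to Day 1 is 14 days if first dose is 15 January, 195 days if 15 July, and 348 days if 15 December. If only the day is missing, the shift is at most about 30 days.

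**The case against.** The strongest counter-argument concerns reach. A reader might infer that adverse events from the placebo period are systematically attributed to idelalisib. The documents do not support that. SAP 7.1.5.1 limits treatment-emergent events to a given study period. SAP 3.5.1 starts the Study 0117 portion at first idelalisib dose for Placebo+R/IDELA and at Study 0117 enrollment for Placebo+R (PD)/IDELA. Protocol 8.6 directs events that are new after Study 0117 consent to Study 0117, so earlier ones are Study 0116 records. An event over by March with idelalisib started in October would plausibly be excluded on these grounds.

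That argument stands in large part, but it is not complete:

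- The study-period boundary is itself a date, and no rule says how a record with a partial onset is assigned to a period.
- For Placebo+R/IDELA, the Study 0117 portion may include data collected in Study 0116 (SAP 3.5.1), so the study identifier does not settle the matter.
- For Placebo+R (PD)/IDELA, the interval between Study 0117 enrollment and first dose lies inside the window.
- SAP 7.4 carries no study-period phrase, so medications are the least protected.

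Other limits also stand. Arm A has no placebo period; its reference date is first idelalisib in Study 0116, so only records from before that dose are exposed. Protocol 10.1.5 requires start and end dates in source records, and 10.2.3 provides automated checks for missing and inconsistent data, so year-only onsets for on-study events may be unusual. Those checks would not expose this contradiction, though: an onset of 2013 and a stop of 10 March 2013 agree with each other until the imputation is applied. Concomitant drugs are summarized only as counts and percentages by preferred name, so day and duration do not matter there. The transaminase resolution analysis (SAP 7.2.5) uses laboratory values, so negative durations arise only for adverse events of interest.

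The convention does err toward over-counting drug events. That is no defense where the stop date already shows the event was over.

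**Conclusion.** The gap is real and minor. As written, SAP 7.1.5.2 gives an impossible result for a record with both a partial onset sharing the year (or month and year) of first idelalisib and a stop date known to precede it. Such a record can become a Day 1 treatment-emergent event or a concomitant drug and, for an adverse event of interest, can have a negative time to resolution. The problem is clearest for concomitant medications and for pre-dose records in the former-placebo groups.

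The number of affected records cannot be derived from the documents. In particular, nothing in them shows that partial medication start dates are common, or that total treatment-emergent counts would move noticeably. The conclusion rests on reading the imputation and classification rules literally, with no unstated stop-date check in the programming. Consequences are confined to descriptive safety and medication summaries; SAP 3.5.2 plans no formal comparisons.

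**What to change.** Add a stop-date condition to SAP 7.1.5.2, which SAP 7.4 then inherits through its existing cross-reference:

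- **Keep the first-dose imputation** when the stop date is missing, the record is ongoing, the stop date is on or after first idelalisib, or the stop date is partial and not clearly earlier (for example, known only to the month or year of first dose).
- **Otherwise**, when a complete stop date precedes first idelalisib, or the known stop month or year ends before it, impute the onset to 1 January or the first of the month, never later than the stop date. Class the event as not treatment-emergent on the onset criterion, or the drug as a prior medication.

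It would also help to say how a record with a partial onset is assigned to a study period under SAP 3.5.1.

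The cost is a sentence or two of text and one condition in the derivation code. No new data are needed. In the worked records, the condition corrects both wrong classifications and leaves the legitimate Day 1 record as it was.

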7.1.6. Summaries of Adverse Events and Deaths

A brief summary of TEAEs by treatment group will show the number and percentage of subjects who (1) had any AE, (2) had any Grade \geq 3 AE, (3) had any IDELA-related AE, (4) had any Grade \geq 3 IDELA-related AE, (5) had any SAE, (6) had any IDELA-related SAE, (7) discontinued from study drug due to an AE, (8) dose interruption due to an AE, (9) dose reduction due to an AE, (10) dose modification (interruption and/or reduction) due to an AE, (11) death due to AEs.

Summaries (number and percentage of subjects) of TEAEs (by SOC, HLT and PT) will be provided by treatment group using the FAS as follows:

- AEs
- AEs by CTCAE Grade
- Grade \geq 3 AE

- IDELA-related AEs
- SAEs
- IDELA-related SAEs
- AEs leading to IDELA modification (reduction and/or interruption)
- AEs leading to IDELA reduction
- AEs leading to IDELA interruption
- AEs leading to permanent discontinuation from IDELA
- AEs leading to death
- TEAE incidence rate adjusted for total exposure

Multiple events will be counted once only per subject in each summary. For data presentation, SOC, HLT and PT will be sorted by decreasing frequency based on IDELA + R/IDELA treatment group. For summaries by severity grade, the most severe event will be selected. In addition to the presentation by SOC and HLT, selected summary will also be presented by preferred term only, ordered by decreasing frequency.

In addition to the by-treatment summaries, data listings will be provided for the following:

- All TEAEs
- SAEs
- AEs leading to discontinuation of IDELA
- Deaths

Relative day from the baseline reference date for safety endpoints, as defined in Section 3.5.1., will be provided for each AE in the listings. The relative day will be calculated as (AE onset date - baseline reference date for safety endpoints + 1).

7.1.7. Treatment-Emergent Adverse Events of Interest

The treatment-emergent AEs of interest (AEI) include:

- **Rash** based on Gilead medical search list including multiple MedDRA preferred terms dermatitis exfoliative, drug eruption, rash, rash erythematous, rash generalised, rash macular, rash maculo-papular, rash papular, rash prutitic, rash morbilliform, and exfoliative rash
- Diarrhea/Colitis including diarrhea or colitis

• Pneumonitis

- Anaphylaxis including anaphylactic reaction, anaphylactic shock, anaphylactic transfusion reaction, anaphylactoid reaction, anaphylactoid shock, circulatory collapse, first use syndrome, kounis syndrome, shock, type I hypersensitivity
- **Bowel perforation** including rectal perforation, duodenal perforation, duodenal ulcer perforation, duodenal ulcer perforation obstructive, diverticular perforation, gastrointestinal perforation, gastrointestinal ulcer perforation, appendicitis perforated, ileal perforation, ileal ulcer perforation, intestinal perforation, intestinal ulcer perforation, jejunal perforation, jejunal perforation, large intestinal ulcer perforation, large intestinal ulcer perforation, small intestinal perforation, small intestinal ulcer perforation

Summaries of TEAEs of interest will be provided for the following:

- AEIs by CTCAE Grade
- AEIs leading to modification (interruption and/or reduction)
- AEIs leading to interruption
- AEIs leading to reduction
- AEIs leading to IDELA discontinuation
- AEIs by time interval (12 weeks intervals)

Incidence and prevalence of AEIs by time interval will be summarized by 12 weeks intervals up to 84 weeks (eg, 0 to < 12 weeks, 12 to < 24 weeks, ..., 72 to < 84 weeks) and \ge 84 weeks. Incidence of AEIs in the interval is defined as the proportion of subjects with onset of AEI in that interval out of those at risk at the beginning of the interval. Prevalence of AEI is defined as the proportion of subjects experiencing AEI in that interval out of those at risk at the beginning of the interval. The subjects at risk include those on IDELA or within 30 days post last dose date for subjects who didn't die at the beginning of the interval.

• Time to first onset and resolution of AEIs

Time to onset of AEIs (in weeks) is defined as time from the baseline reference date for safety endpoints to the date of first incident of AEI. In the absence of an event, the onset date will be censored at the earliest from the following dates: last IDELA dosing date (ie, captured on study drug completion CRF page) + 30 days, analysis data cut-off date and death date. Time to resolution of AEIs is calculated as (AEI stop date – start date of first occurrence of AEI + 1) / 7.

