5.4.2.1. Investigation for Idelalisib Late Onset or Severe Diarrhea/Colitis

See CTCAE Version 4.03 for definitions of colitis and diarrhea.

Among idelalisib-treated patients who reported diarrhea or colitis, the median time to onset of any grade diarrhea or colitis was 1.9 months (range, 0.0–29.8), of grade 1 or 2 was 1.5 months (range, 0.0–15.2) and of grade 3 or 4 was 7.1 months (range, 0.5–29.8). Kaplan–Meier curves of time to onset of diarrhea or colitis are shown for all idelalisib- treated patients in Figure 5-1 {Coutre 2015}.

Figure 5-1. Kaplan-Meler Time to Diarrhea or Colitis

Idelalisib-associated severe diarrhea responds poorly to antimotility agents however, median time to resolution ranged between 1 week and 1 month across trials following interruption of idelalisib treatment and, in some instances, initiation of corticosteroid treatment {Gilead Sciences Inc 2014}.

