2. TYPE OF PLANNED ANALYSIS

The data monitoring committee (DMC) will have access to serious adverse events requiring expedited reporting and will be provided with accumulating safety data on a regular basis. Interim safety reviews will be conducted by the DMC in conjunction with safety reviews of the primary clinical trial (Study GS-US-312-0116), if applicable, at intervals of ~6 months; the specific frequency of these reviews will depend upon the rate at which the trials are enrolled, the nature of any emerging safety signals, and monitoring recommendations from the DMC. At each review, all available safety data will be summarized and evaluated.

The efficacy analysis of the blinded portion of this clinical trial (Study GS-US-312-0117) is planned to take place at the time of the final analysis of the blinded portion of the primary study (GS-US-312-0116). Once outstanding data queries have been resolved, the database will be finalized for the blinded portion, and the blind will be broken.

Following unblinding, interim and final analyses are planned to be performed in support of regulatory review of data from the primary study. An analysis of efficacy and safety may be included to satisfy regulatory requirements and to perform long-term efficacy, safety, and OS follow-up. The timing of the final analysis is expected to occur within 48 months of accrual of the final subject to Study GS-US-312-0117.

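### The open interval from week 84 in SAP 7.1.7 cannot be read against the fixed 12-week intervals of the AEI incidence and prevalence tables

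*SAP*

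**What the plan says.** SAP 7.1.7 plans two tables of adverse events of interest (AEIs) by time on drug: 3.1.24.6 for incidence and 3.1.24.7 for prevalence. "Incidence and prevalence of AEIs by time interval will be summarized by 12 weeks intervals up to 84 weeks"; everything from week 84 onward goes into one further cell. That makes seven closed cells of 12 weeks and one open cell.

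Incidence is the "proportion of subjects with onset of AEI in that interval out of those at risk at the beginning of the interval". Prevalence is the "proportion of subjects experiencing AEI in that interval out of those at risk at the beginning of the interval". On the denominator, "The subjects at risk include those on IDELA or within 30 days post last dose date", provided they are alive when the interval starts. Neither definition uses the time a subject is actually observed within the interval.

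Three other provisions set how long the open cell can be:
- Treatment has no fixed end (SAP 1.2, Study Duration).
- "The timing of the final analysis is expected to occur within 48 months of accrual of the final subject" (SAP 2). SAP 1 covers interim as well as final analyses.
- For safety, time runs from the first idelalisib dose. For subjects randomized to Arm A that dose was in GS-US-312-0116; for the placebo groups it came later (SAP 3.5.1, Table 3-1).

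**The concern.** These tables set AEI risk in successive periods side by side. A reader will compare the last column with the seven before it. A proportion over a long period is larger than a proportion over 12 weeks even when the underlying risk is unchanged, so the comparison mixes risk with interval length. The same applies across treatment groups if they have different amounts of follow-up past week 84.

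At stake is the reading of late toxicity. Protocol 5.4.2.1 reports, from a cited publication, that the median onset of diarrhea or colitis "of grade 3 or 4 was 7.1 months (range, 0.5–29.8" months). The upper end of that range is about 130 weeks, so late onsets of this kind would fall in the open cell. A real late increase there could not be told apart from the effect of interval length.

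**Working it through.** The plan gives no AEI rate for these tables, so there is no figure to reproduce. The check asks what the tables would show if the risk did not change at all.

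**From the documents.** Closed cell: 12 weeks. Open cell: from week 84 (19.3 months). Final analysis up to 48 months after last accrual: 48 × 30.4375 / 7 = 208.7 weeks. A last-enrolled subject who starts drug at enrollment and stays on it can therefore contribute 208.7 − 84 = 124.7 weeks to the open cell.

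**Assumed, because the documents do not say.** AEI risk of 2%, 5% or 10% per 12 weeks; no discontinuation, or median time on drug of 24, 12 or 6 months; mean event duration of 4 weeks for prevalence.

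**Formula.** With constant AEI hazard λ = −ln(1 − p)/12 per week, constant discontinuation hazard μ = ln 2 / median, and interval length L, the expected proportion is λ/(λ+μ) × [1 − exp(−(λ+μ)L)].

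**Example.** p = 5% gives λ = 0.00427; a median of 12 months (52.2 weeks) gives μ = 0.01328; λ/(λ+μ) = 0.243.
- L = 12: 0.243 × (1 − e^−0.211) = 4.6%.
- L = 124.7: 0.243 × (1 − e^−2.19) = 21.6%.
- Ratio 4.7, with no change in risk.

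**Results at 5% per 12 weeks, 124.7 weeks available:**

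| Median time on drug | 12-week cell | Open cell | Ratio |
|---|---|---|---|
| No discontinuation | 5.0% | 41.3% | 8.3 |
| 24 months | 4.8% | 29.1% | 6.1 |
| 12 months | 4.6% | 21.6% | 4.7 |
| 6 months | 4.3% | 13.6% | 3.2 |

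Over all the assumed risks and discontinuation rates the ratio is 2.9 to 9.5 with 124.7 weeks available, 2.4 to 4.2 with 52 weeks, and 1.7 to 2.0 with 24 weeks.

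**Simulation.** 60,000 subjects, 5% risk, the SAP's numerators and denominators including the 30-day tail:
- Period prevalence, closed against open cell: about 6.7% against 42% with no discontinuation, 6.2% against 23% at a median of 12 months, 6.0% against 14% at 6 months.
- Counting first onsets only, median 12 months: 3.2% in weeks 72 to 84 against 15.8%.
- Early data cut, median 12 months: with a mean of 10.8 weeks at risk after week 84, the open cell shows 4.4% against 4.8% in weeks 72 to 84; with 5.7 weeks it shows 2.3% against 4.8%. The error then reverses.

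**Does person-time remove it?** Expected person-time to the first of onset, discontinuation and L is [1 − exp(−(λ+μ)L)]/(λ+μ). Dividing the expected proportion by this gives λ, whatever L is. At 5% that is 0.00427 × 52.18 × 100 = 22.3 per 100 patient-years. The simulation (median 12 months, all events over all time at risk) gave 21.2 to 22.7 in the closed cells and 22.0 in the open one. Continuing 12-week cells gave 4.4% to 4.8% from week 84 to about week 180, against 4.5% to 5.0% before week 84.

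**The case against.** The strongest reply is that these tables are not the only evidence on timing. SAP 7.1.7 also plans time to first AEI onset, censored at the earliest of last dose plus 30 days, data cut-off and death (Table 3.1.24.8). SAP 7.1.8 plans an exposure-adjusted AEI rate (Table 3.1.24.9), and the listings give the relative day of each event. The analyses are descriptive (SAP 3.5.2), and the open column is labelled as such. Pooling a sparse tail is a reasonable choice with 161 subjects enrolled. All of this stands and limits the harm. It does not correct the tables: the exposure-adjusted rate is one figure per group, the onset summary covers first events only, and the planned Kaplan-Meier onset curve is for transaminase elevation, not for AEIs.

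The constant-risk premise can also be challenged, since Protocol 5.4.2.1 puts median onset of any-grade diarrhea or colitis at 1.9 months. A falling hazard would shrink the apparent rise. At 5% risk with 124.7 weeks available, however, the hazard after week 84 would have to fall to 0.10 (no discontinuation), 0.18 (median 12 months) or 0.29 (median 6 months) of its earlier value before the open cell merely matched a 12-week cell.

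A reader might infer that the last column must rise. The documents do not support that: 48 months is an upper limit, interim analyses are planned, and a short at-risk time after week 84 gives a drop. A reader might also infer that this trial's late colitis is known to fall in the open cell. The 29.8 months is the maximum of a range from a cited publication; the median for grade 3 or 4 in the same sentence, 7.1 months (about week 31), lies in a closed cell.

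The denominator also keeps subjects who are in the 30-day tail or stop drug during a cell. This matters little within 12 weeks: at 3% risk and median time on drug of 52 to 104 weeks, the cell shows 2.8% to 2.9%.

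**Conclusion.** The concern holds as a defect of two descriptive tables. As defined, the cell from week 84 cannot be compared with the 12-week cells, or between groups whose time past week 84 differs. With substantial follow-up it shows a false rise under constant risk: roughly 3- to 9-fold with about 124 weeks available, about 2-fold with 24 weeks. If mean at-risk time after week 84 is under about 12 weeks, it can show a false drop.

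The lack of comparability follows from the SAP text alone. The size and direction rest on assumed event and discontinuation rates and on time on drug past week 84, none of which the documents give. No formal test is affected, and the SAP's other AEI summaries give partial protection. The change is worth making because it is cheap and uses a method the SAP already has in 7.1.8.

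**What to change.** **Incidence (SAP 7.1.7, Table 3.1.24.6).** For each interval, including the open one, report subjects with onset divided by person-time at risk in that interval, with the number at risk at its start. End a subject's person-time at the earliest of first onset in the interval, last dose plus 30 days, death, data cut-off and the end of the interval. The rate in the open cell is still an average over its whole span.

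**Prevalence (Table 3.1.24.7).** Continue equal 12-week intervals past week 84 and show the number at risk in each. If a final open cell is kept, add a footnote that it is not to be read against the 12-week cells.

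**Cost.** SAP wording and minor programming for two tables, with no new data or procedures. The downside is some sparse late columns.

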7.1.8. Exposure-adjusted TEAE Rate

The exposure-adjusted TEAE rate is defined as the number of subjects with a specific event divided by the total exposure-time among the subjects in the treatment group and at risk of an initial occurrence of the event. Specifically,

Exposure-Adjusted TEAE Rate $= \frac{n}{T} = \frac{n}{\sum t_i}$

Where *n* is the number of subjects with events, t_i is the i^{th} subject exposure time in years and *T* is the total exposure time in years of all subjects. If a subject has multiple events, the t_i is the time of the first event. For a subject with no event, the t_i will be censored at the time of data cut-off date if the subject is still taking IDELA; and the t_i will be censored at the time of last does date plus 30 days or data cutoff date whichever is earlier if the subject discontinues IDELA.

The exposure-adjusted TEAE rate will be summarized for AEI by treatment group based on the FAS.

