7.2.5. Transaminase Elevations

Analyses of transaminase elevations will be based on laboratory values using the FAS. Number and percentage of subjects will be summarized by treatment groups for subjects:

- with Grade 3 or 4 alanine aminotransferase (ALT)/aspartate aminotransferase (AST) elevation
- with Grade 3 or 4 ALT/AST elevation resolved to both ALT/AST of Grade 1 or less
- re-challenged after dose interruption
- with recurrence of Grade 3 or 4 ALT/AST elevation among re-challenged
- with recurrent Grade 3 or 4 ALT/AST elevation resolved to both ALT/AST of Grade 1 or less

Kaplan-Meier curves and estimates will be provided for time to onset of first Grade 3 or 4 treatment-emergent ALT/AST elevations. Time to onset of first event is defined as time from the baseline reference date for safety endpoints to the start date of first Grade 3 or 4 treatment-emergent ALT/AST elevation, ie, time in weeks is calculated as (start date of first occurrence – baseline reference date for safety endpoints + 1) / 7. In the absence of an event, the censoring date applied will be the earliest from the following dates: last dose date (if treatment discontinued) + 30 days, analysis data cut-off date and death date.

For subjects with at least 1 episode of Grade 3 or 4 ALT/AST elevation, time to resolution of the first episode of treatment-emergent Grade 3 or 4 ALT/AST elevation to Grade 1 or less will be summarized using Kaplan-Meier estimates. The same censoring rule described above for time to onset will be used.

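### No Grade ≥3 onset, interval or exposure-adjusted summary is planned for diarrhea/colitis, although the protocol reports that severe cases begin much later than mild ones

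*SAP*

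**What the plan says.** SAP 7.1.7 defines the Diarrhea/Colitis AEI as one pooled category, "including diarrhea or colitis", without a grade criterion. Its time-based analyses, and the related rate in SAP 7.1.8, are as follows.

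- **Onset:** "time from the baseline reference date for safety endpoints to the date of first incident of AEI". Subjects without an event are censored, but no estimator is named.
- **Resolution:** "AEI stop date – start date of first occurrence of AEI + 1) / 7", so it is anchored on the first occurrence.
- **Interval incidence:** "Incidence of AEIs in the interval is defined as the proportion of subjects with onset of AEI in that interval". The denominator is everyone still on drug, or within 30 days of the last dose, when the interval starts. The tables are "summarized by 12 weeks intervals up to 84 weeks", followed by one open-ended row for week 84 onward.
- **Exposure-adjusted rate (SAP 7.1.8):** "If a subject has multiple events, the t_i is the time of the first event".

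In SAP Appendix 1, the titles of Tables 3.1.24.6 to 3.1.24.9, which hold these results, carry no grade. Tables 3.1.24.1 to 3.1.24.4 do carry grade but have no time dimension.

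For liver enzymes the same SAP (7.2.5) does time the severe event: "Kaplan-Meier curves and estimates will be provided for time to onset of first Grade 3 or 4 treatment-emergent ALT/AST elevations".

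Protocol 5.4.2.1 gives median onset of diarrhea or colitis as 1.9 months for any grade and 1.5 months for Grade 1–2. The median "of grade 3 or 4 was 7.1 months (range, 0.5–29.8").

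**The concern.** The protocol describes two onset patterns: common mild diarrhea in the first weeks, and severe diarrhea or colitis typically some months later. An analysis that takes the first event of any grade mostly reports the first pattern. Protocol 3.1.5 includes severity and timing of onset in the safety endpoint. Protocol 3.2.5 names gastrointestinal inflammation as a parameter of specific interest and promises extra scrutiny of Grade 3–4 events.

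An extension study with prolonged continuous dosing is well placed to show when severe diarrhea/colitis starts and whether the risk continues. As planned, no summary table or curve does that.

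**Working it through.** **1. Place the protocol's figures on the SAP's time scale.** One month is 365.25 / 12 / 7 = 4.348 weeks.

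| Onset figure (Protocol 5.4.2.1) | Months | Weeks | SAP row |
|---|---|---|---|
| Median, Grade 1–2 | 1.5 | 6.5 | 0 to <12 |
| Median, any grade | 1.9 | 8.3 | 0 to <12 |
| Median, Grade 3–4 | 7.1 | 30.9 | 24 to <36 |
| Latest Grade 3–4 | 29.8 | 129.6 | ≥84 |

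The any-grade median lies close to the Grade 1–2 median and far from the Grade 3–4 median. An any-grade first-event summary therefore mainly describes mild events.

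**2. How far is the onset of severe cases displaced?** Let q be the share of severe cases who also have separately recorded mild diarrhea. The documents do not give q, so it is varied from 0 to 1. Assume exponential onset with medians a = 6.52 weeks (mild) and b = 30.87 weeks (severe), independent of each other. The SAP records the earlier of the two, so the probability that no onset has been recorded by week t is

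S(t) = 2^(−t/b) × [(1 − q) + q × 2^(−t/a)].

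The median recorded onset solves S(t) = 0.5. Among subjects whose severe event starts at or after week 12, the share given an onset before week 12 is q × (1 − 2^(−12/6.52)) = q × (1 − 0.279) = 0.72q.

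| q | Median recorded onset, severe cases (weeks) | Late severe cases recorded before week 12 |
|---|---|---|
| 0 | 30.9 | 0% |
| 0.25 | 19.8 | 18% |
| 0.50 | 11.5 | 36% |
| 0.75 | 7.4 | 54% |
| 1 | 5.4 | 72% |

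With a Grade ≥3 definition the median is 30.9 weeks for every q.

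**3. The interval tables.** Take a subject with Grade 1 diarrhea in month 1 and a separate Grade 3 colitis at month 8 (8 × 4.348 = 34.8 weeks). Under SAP 7.1.7 the earlier event does not remove the subject from the denominator, and the definition is not limited to first onsets. Read literally, the colitis counts in the 24 to <36 week row, but that row does not show that it was severe. Time to onset and the AEI exposure-adjusted rate use month 1.

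**4. The last row.** Week 84 is 84 / 4.348 = 19.3 months. From there to week 129.6 is (129.6 − 84) / 12 = 3.8, or about four 12-week intervals. If the true risk were a constant 2% per interval (an assumption) with no dropout, the open row would show 1 − 0.98^4 = 7.8% over four intervals, or 1 − 0.98^7 = 13.2% over seven, beside 2% in each earlier row.

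**The case against.** A reader might infer that severe colitis is hidden, or is never timed. The documents do not support that.

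- The interval tables count later episodes in their own rows (step 3). The once-per-subject counting rule in SAP 7.1.6 leaves some doubt about repeats, but the AEI definition itself is not first-onset only.
- Severe cases appear in the by-grade AEI tables (3.1.24.1 to 3.1.24.4) and in the Grade ≥3 tables (3.1.5 and 3.1.15). SAP 7.1.6 also gives a relative onset day for each event in the listings.
- SAP 7.1.6 lists an exposure-adjusted rate among the summaries by preferred term, and Table 3.1.23 is separate from the AEI version. If it is run by term, a colitis following a diarrhea would have its own event time.

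Other points on this side also stand. The masking depends on an unknown q. The medians come from a pooled external population, so 7.1 / 1.9 = 3.7 is not a within-subject distortion. The analyses are descriptive, and the extra table could be produced later from data already collected. With 161 subjects enrolled and three reporting groups, Grade ≥3 counts per interval will probably be sparse.

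What remains is that a listing gives no median, curve or rate, and no planned time-based summary of Diarrhea/Colitis isolates severe events. The any-grade interval rows can show that onsets continue, but not that severe ones do.

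**Conclusion.** The concern holds as a gap in the planned summaries, not as a loss of data. For Diarrhea/Colitis, onset, resolution and the AEI exposure-adjusted rate rest on the first event of any grade, and the interval tables are not split by grade. On the protocol's figures, the onset summary would centre near 8 weeks, while severe events centre near 31 weeks. This assumes that timing in this study resembles that in the patients described in Protocol 5.4.2.1.

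The displacement of severe cases' own recorded onset ranges from none (q = 0) to a median of 5.4 weeks instead of 30.9 (q = 1), under independent exponential onsets. Even at q = 0, the summary over all subjects still mixes mild and severe events.

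A reader might also extend the point to Rash and Pneumonitis. The documents give grade-dependent onset times only for diarrhea/colitis, so that extension is not supported. This is a low-cost improvement; no planned result is invalid without it.

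**What to change.** In SAP 7.1.7, SAP 7.1.8 and the matching tables, for Diarrhea/Colitis:

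1. Add time to first Grade ≥3 onset with Kaplan-Meier estimates, on the pattern of SAP 7.2.5.
2. Add Grade ≥3 incidence per 12-week interval.
3. Add a Grade ≥3 exposure-adjusted rate, with t_i stopped at the first Grade ≥3 event.
4. Keep the at-risk and censoring rules of the any-grade analyses.
5. Continue the 12-week rows past week 84, or give a person-time rate for the last row, because an open-ended proportion is not comparable with 12-week proportions.

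The cost is SAP wording and a few table runs on grade and onset dates that are already collected; some cells will be sparse. There is one real limit. Protocol 8.5 records a single maximum grade per episode, so an episode that worsens from mild to severe keeps its original start date. Only severe episodes recorded separately will be re-timed, and the table footnote should say so.
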